## 8. STUDY OBJECTIVES

### **Primary Objective**

The primary objective is to determine the safety of SPN-812V in adults with ADHD.

### Secondary Objectives

The secondary objectives of this study are:

- To determine the efficacy of SPN-812V in adults with ADHD
- To explore the single dose and steady state pharmacokinetics of SPN-812V in adults with ADHD.

### 9. INVESTIGATIONAL PLAN

### 9.1. Overall Study Design and Plan

This will be a multicenter, randomized, double-blind, placebo-controlled, parallel group study of the safety and efficacy in adults with ADHD. The target subjects are healthy male or female adults aged 18 to 64 years, inclusive, with a diagnosis of ADHD. A total of fifty subjects will be enrolled at approximately 5 sites in the US. Subjects will be randomized (1:1) to one of two treatment groups, SPN-812V or placebo.

The study will consist of a Screening Period (within 14 days prior to randomization) and a Dosing Period of 6 weeks,. The total subject duration in the study will be up to 8 weeks as illustrated in Figure 1.

Supernus Pharmaceuticals, Inc. SPN-812V - 812P201

[figure not shown]

Figure 1. Study Schematic

## 9.1.1. Screening Period

Screening will take place within 14 days prior to randomization to determine subjects' eligibility to participate in the study. No screening or study-specific assessments may be performed until written informed consent has been obtained. Screening procedures will be performed to determine each subject's eligibility to participate in the study and may be carried out over more than one visit during the Screening Period. Abnormal results on laboratory tests may be repeated once at the discretion of the Investigator during the Screening Period.

Additional screening procedures will include review of medical and psychiatric history, including confirmation of ADHD diagnosis and smoking history; assessment of suicide risk; assessment of demographic and baseline characteristics; full physical examination; measurement of vital signs, height and weight; ECG; sample collections for hematology, biochemistry, CYP2D6 enzyme activity screening, urinalysis, urine drug screen and serum pregnancy test (FOCP only); prior and concomitant medication information will also be collected.

### 9.1.2. Dosing Period

Subjects who meet the requirements for study participation will be randomized and proceed to the Dosing Period which will last 6 weeks. Approximately 50 subjects will be randomized at a 1:1 ratio, using a centralized randomization system, to either SPN-812V or placebo. The first dose of SM should be taken the morning after the randomization visit.

At the baseline and randomization visit, baseline safety and efficacy assessments will be performed. Inclusion/Exclusion criteria should be re-assessed at this visit. Concomitant medication information will be collected. FOCP will be given a urine pregnancy test. SM will be dispensed.

Each week after randomization, subjects will return to the study site for monitoring of AEs, and the administration of safety tests and efficacy scales. Procedures to be performed are collection

CONFIDENTIAL Version 2.0

of vital signs and weight, PK blood sampling at Visit 8 (optional, if subjects wish to participate), and an ECG at Visit 4. Assessments of concomitant medications, suicide risk, and SM compliance and dispensation will be performed. Subjects who have consented to participate in the optional PK sub study will be given a diary at Visit 7 on which to record time of SM doses taken prior to Visit 8. Subjects who are participating in the optional PK sub study will be given all efficacy assessments prior to blood draws or dosing on the PK day. For subjects not participating in the optional PK sub study, their last dose will be taken the evening before the End of Study Visit (Visit 8).

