## 9.4.3. Pharmacokinetic Measurements

On the morning of Visit 8, all subjects who wish to participate in the optional PK day will arrive at the clinic after an overnight fast and will have all efficacy assessments administered first. The subjects then will have a pre-dose PK sample taken, and be administered either 2 x 50mg SPN-812V capsules or will be administered 1 x 50mg SPN-812V capsule for subjects who underwent dose reduction. PK sampling will occur pre-dose and at 0.5, 1, 2, 3, 4, 5, and 6 hours post-dose. Although there is a 30 minute window on draw times, efforts should be made to ensure that the time interval between any two sampling timepoints is not less than 30 minutes. Subjects may eat two hours after dosing.

SPN-812V concentrations in plasma samples will be determined by the Sponsor using a validated chromatographic method. The amount of blood to be drawn at each timepoint to determine the plasma concentrations of SPN-812V is 4mL. Information regarding sample collection, handling, and shipping procedures will be detailed in a separate manual.

Single dose administration of viloxazine hydrochloride (100mg) to ten healthy volunteers resulted in mean  $C_{max}$  near 1800 ng/mL for viloxazine at a mean  $T_{max} \sim 100$  min post-dose and with elimination half-life ~3 hr (Vandel B. et al., "Pharmacokinetics of viloxazine hydrochloride in man," European Journal of Drug Metabolism and Pharmacokinetics, 1982, Vol 7, pp. 65-68). Timepoints were chosen on the basis of these data to inform both absorption and elimination phases of the viloxazine time course while minimizing the sampling burden on patients. The design of the study provides both first-dose (in placebo group) and steady state (in active group) observations, albeit in parallel treatment groups.

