# 9.4.4.6. Electrocardiograms (ECGs)

ECGs (12-lead) will be obtained at the Screening Visit, Visit 4, and the Final Visit as designated on the Schedule of Visits and Procedures (Table 1. Schedule of Visits and Procedures). Additional ECGs may be performed at other times if deemed necessary.

The ECG will be recorded while the subject is resting in a supine position. The ECG will electronically measure the PR, QRS, QT, and QTc intervals, and heart rate.

All ECG tracings will be reviewed within 24 hours by the Investigator or qualified Sub-Investigator. PR intervals will be determined for each of these ECGs from a single reading. Invalid measurements will be repeated. QTc will be reported as QTcF (QT corrected using Fridericia's method).

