## 9.5. Treatments

#### 9.5.1. Treatments Administered

SM will be dispensed at each visit during the Randomization and Dose Treatment Periods. Subjects will receive a bottle at each visit containing the correct number of 50mg (or placebo) capsules, which is a sufficient number of capsules for dosing until the next visit. The SM will be taken by the subject orally, three times per day during waking hours, with at least 4 hours between doses (morning, noon, and evening).

At Visit 8, subjects who agree to participate in the optional PK sub study will be given 2 x 50mg SPN-812V capsules on-site in the morning, unless the subject had been down-titrated, in which case, the subject will receive 1 x 50mg SPN-812V capsule on-site in the morning. Note: all subjects who participate in the optional PK sub study will be given active SPN-812V capsule(s) in this portion. For subjects not participating in the optional PK sub study, their last dose will be taken the evening before the End of Study Visit (Visit 8).

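### Outside the PK sub-study the final ECG is taken near drug washout, the Visit 4 ECG has no set time after a dose, and Visit 8 readings mix different dosing states.

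*Protocol*

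**What the plan says.** **Last dose.** Protocol 9.1.2 states that for subjects not in the optional PK sub-study "their last dose will be taken the evening before the End of Study Visit (Visit 8"). The synopsis, Protocol 9.5.1 and SAP 3.1.2 repeat this. On other days the drug is taken "three times per day during waking hours, with at least 4 hours between doses (morning, noon, and evening"), with no clock times.

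**ECGs.** Protocol 9.4.4.6: "ECGs (12-lead) will be obtained at the Screening Visit, Visit 4, and the Final Visit". It fixes posture ("The ECG will be recorded while the subject is resting in a supine position") but no time after dose, and it allows unscheduled tracings: "Additional ECGs may be performed at other times if deemed necessary". Note b to Table 1 in Protocol 9.4.1 places end-of-study procedures at the end of Visit 8 unless already done during that visit, or at early discontinuation.

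**Vital signs.** Table 1 has them at every visit. Note d times them only to scheduled blood draws, where there are any.

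**Drug kinetics.** Protocol 9.4.3 cites a single-dose study in ten healthy volunteers with a mean Tmax of about 100 minutes and "elimination half-life ~3 hr".

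**PK sub-study.** Participants skip their morning dose at home. On site they take active drug whichever arm they were randomized to (Protocol 9.5.1 and 9.5.5). Only they are given a diary of dose times.

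**Analysis.** SAP 6.3 and 6.4 summarise vital signs and ECG by visit and treatment group. Neither section uses time since dose or PK participation.

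**The concern.** The synopsis places the primary safety endpoint, and the ECG and vital-sign analyses that serve it, after six weeks of treatment. Visit 8 is that time point. For most or all subjects outside the PK sub-study, it is also a time when little drug remains.

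That leaves Visit 4, about a week after titration to the study dose, as the only other scheduled on-treatment ECG. Nothing says whether it is taken before that day's dose or near its peak. If an ECG effect follows plasma concentration, a reassuring result at either visit could reflect when the tracing was taken.

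Visit 8 has a second difficulty. It can combine readings taken after an overnight gap, readings taken hours after an on-site dose, and readings from placebo subjects who have just had active drug. The planned table does not separate them, so the placebo column may not be drug-free.

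**Working it through.** The documents state no gap or residual level, so there is no plan figure to reproduce.

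**Inputs from Protocol 9.4.3:** half-life 3 h; Tmax 100 min = 1.67 h. The source is described as "Single dose administration of viloxazine hydrochloride (100mg) to ten healthy volunteers resulted in mean" values, so these are single-dose figures in volunteers, not patients.

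**Assumptions:** dose times, visit times, one-compartment kinetics and linear accumulation.

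**Step 1, half-lives.** Number = gap / 3; fraction left by simple decay = 0.5^(gap/3).
- 10 h: 3.3 half-lives, 10% left
- 12 h: 4.0, 6%
- 15 h: 5.0, 3%
- 18 h: 6.0, 1.6%

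With a half-life of 2.5-3.5 h, a 12-15 h gap is 12/3.5 = 3.4 to 15/2.5 = 6.0 half-lives.

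**Step 2, level relative to steady-state peak.** This allows for absorption and for earlier doses. ke = ln 2 / 3 = 0.231 per h. Solving ln(ka/ke)/(ka - ke) = 1.67 h gives ka = 1.24 per h. Each dose contributes c(t) = ka/(ka - ke) x [exp(-ke t) - exp(-ka t)], and contributions are summed.

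Example: doses at 08:00, 13:00 and 20:00, none on the visit day, assessed at 08:00. The previous day's doses are 12, 19 and 24 h old and contribute 0.077 + 0.015 + 0.005 = 0.097. The daily peak on the same scale is 0.974, and 0.097/0.974 = 10%.

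| Assumed doses | Assessed | Gap (h) | Half-lives | % of peak |
|---|---|---|---|---|
| 08:00, 12:00, 18:00 | 08:00 | 14 | 4.7 | 6.3 |
| 08:00, 12:00, 18:00 | 11:00 | 17 | 5.7 | 3.1 |
| 08:00, 13:00, 20:00 | 08:00 | 12 | 4.0 | 10.0 |
| 08:00, 13:00, 20:00 | 11:00 | 15 | 5.0 | 5.0 |
| 08:00, 13:00, 20:00 | 14:00 | 18 | 6.0 | 2.5 |
| 08:00, 14:00, 22:00 | 08:00 | 10 | 3.3 | 15.9 |
| 08:00, 14:00, 22:00 | 11:00 | 13 | 4.3 | 8.0 |

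**Step 3, Visit 4.** With doses taken as usual at 08:00, 13:00 and 20:00, the level is about 10% of peak at 08:00 before the dose, 75% at 10:00 and 98% at 14:00. The plan allows any of these.

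**Step 4, PK participants at Visit 8.** Before the on-site dose they too have had an overnight gap. If the ECG follows the 6 h draw, the level from that dose alone is c(6)/c(1.67) = 45% of a single-dose peak, falling to 36% at 7 h. This applies to placebo subjects as well.

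**The case against.** Several stronger readings are tempting, and the documents do not support them.

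- **That low Visit 8 values dilute the whole on-treatment record.** They do not. SAP 6.3 and 6.4 tabulate each visit separately. The outlier table (14.3.5.4) counts any QTcF of at least 500 msec or any change of at least 60 msec across assessments, so a quiet Visit 8 cannot cancel an earlier outlier.
- **That all cardiovascular data are trough data.** The evening-before instruction applies only to Visit 8, and no morning dose is withheld before Visits 3-7. Untimed is not the same as trough. Five vital-sign sets precede Visit 8. On a natural reading of note d, PK participants' vital signs are also taken just before each PK draw, including those around Tmax.
- **That the lost effect can be put in milliseconds.** The documents give no effect size, no expected PK uptake and no concentration-effect relation, so no such figure can be derived.
- **That dose times are not collected at all.** The eCRF is a separate document, and Protocol 9.5.11 has unblinded staff keep dosing records. What can be said is that the protocol and SAP specify no dose-time record outside the PK diary and no time-since-dose variable.

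It is also fair to say that this is a proof-of-concept study of about 50 subjects with descriptive safety p-values, that it does not claim to exclude a QT effect, and that unscheduled or early-termination ECGs may fall nearer a dose. Those ECGs are not systematic, however. With safety as the primary objective and two scheduled post-baseline ECGs, knowing when they were taken relative to dosing is basic to reading them.

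The SAP's rule of analysing safety by treatment actually received does not settle the Visit 8 problem, because it does not say how a placebo subject is classed after the on-site active dose.

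**Conclusion.** The concern holds for the ECG. Outside the PK sub-study the final scheduled ECG follows a gap of roughly 3.3-6 half-lives. The modelled level is about 3-16% of steady-state peak for last doses at 18:00-22:00 and assessment at 08:00-11:00. Visit 4 could fall anywhere from about 10% to 98% of peak under one plausible dosing pattern. A concentration-related effect could therefore be missed; an effect that does not follow plasma level would be less affected. Nothing here says that such an effect exists.

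For vital signs the same weakness applies at Visit 8 but matters less, because Visits 3-7 supply on-treatment readings, although untimed.

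The mixing of Visit 8 readings is a separate defect that does not depend on the modelling: it follows from giving active drug to PK participants in both arms and leaving the order of ECG and dose open. For the same reason it would be wrong to label every Visit 8 reading as trough.

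The percentages rest on assumed clock times and on single-dose kinetics from ten volunteers. Across the ranges tried, the final ECG outside the PK sub-study stays at or near washout.

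**What to change.** Leave dosing as it is.

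1. **Data collection.** Record the time of last dose and the clock time with every ECG and vital-sign set.
2. **Visit 4.** Take the ECG and vital signs in a fixed window after that day's dose, wide enough to span the protocol's Tmax of about 100 minutes.
3. **SAP 6.3 and 6.4, on-drug comparisons.** Make Visit 4 the main on-drug ECG comparison. Use Visits 4-7 for vital signs at the study dose, and show Visit 3, which follows the starting-dose week, separately.
4. **SAP 6.3 and 6.4, Visit 8.** Present Visit 8 by PK participation and by whether the reading preceded or followed the on-site dose. Label only non-PK and pre-dose readings as trough. Exclude post-dose readings of placebo-arm PK participants from the placebo comparison.

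The cost is one extra CRF field for the time of last dose (plus the clock time where it is not already captured), a visit-timing instruction, some SAP wording, and less freedom in booking the Visit 4 appointment. One limitation remains: with dosing unchanged, there is still no near-peak ECG at six weeks outside the PK sub-study, and the study report should say so.

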# 9.1.3. End of Study Visit/Early Termination

At the end of Visit 8, or prior to early discontinuation, subjects will undergo end of study assessments. AEs will be monitored, and safety tests and efficacy scales will be administered unless assessments were performed earlier in the visit. The procedures to be performed will include physical examination, collection of vital signs, weight, ECG, blood collection for hematology and chemistry, urine collection for urinalysis, drug screen, and pregnancy test (for FOCP). Assessments of concomitant medications and SM compliance will be performed.

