### Treatment Schedule (Procedure):

Screening (Visit 1): Subjects will undergo initial screening evaluation after informed consent is obtained, including complete medical and psychiatric history, physical exam, serum pregnancy test (FOCP only), routine laboratory assessment and genetic testing for CYP2D6 enzyme activity, smoking status, and urine drug screen. Confirmation of ADHD will be performed with the CAADID and the CGI-S will be administered. Study qualification requirements will be reviewed to confirm that the subject meets all inclusion and exclusion criteria.

Baseline and Randomization and dispensation of SM (Visit 2): After a screening period of up to 14 days subjects will return to the investigational site and undergo their scheduled baseline assessment. If their eligibility to participate in the trial is confirmed, subjects will be randomized (1:1) to receive a starting dose of 1x50 mg capsule TID (150 mg/day) of either SPN-812V or placebo. Subjects will receive treatment at the 150 mg/day starting dose for one week. Dosing is to start the morning after Visit 2. Subjects who do not tolerate the starting dose will be discontinued from the study.

Study Dose Treatment Phase (Visits 3 – 8): Subjects who tolerated the starting dose will then be titrated to receive a study dose of 2x50 mg TID (300mg/day) and continue this treatment regiment for five weeks. Subjects who, after titration to the study dose, do not tolerate treatment at 300 mg/day, will be allowed, at any time, to down-titrate the dose to the 150 mg/day starting dose and continue treatment at the same dose until completion of the study. Subjects will return to the investigational site once a week to undergo safety and efficacy evaluations and to have SM compliance checked. At the end of Visit 7, the subjects who have consented to participate in the optional PK sub study will receive a drug diary to record times of all weekly doses, will be instructed to fast the night before Visit 8, and will be instructed to not take SM that morning. At Visit 8, subjects who agree to participate in the optional PK sub study will receive SM dose and will have blood drawn for PK assessments over approximately seven hours. All rating scales will be administered prior to PK dosing and blood draws. For subjects not participating in the optional PK sub study, their last dose will be taken the evening before the End of Study Visit (Visit 8).

[figure not shown]

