End of Study: At the end of the Visit 8 procedures or at early termination, subjects will complete end of study assessments. Subjects will return any unused capsules and undergo safety and efficacy evaluations if not already performed as part of that visit.

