### 9.4. Study Methods

### 9.4.1. Schedule of Visits and Procedures

Table 1. Schedule of Visits and Procedures presents the schedule of visits and procedures for the study.

Study Phase	Screening	Dose Treatment Period		End of Study b
	Period	(Visit window +/- 2 days)		
Activity	Visit 1 Up to 14 Days Prior to Visit 2	Visit 2	Visits 3 – 8	
Informed Consent a	Х			
Medical and Psychiatric History and Demographics	х			
Physical Exam	Х			Х
ECG (12-lead)	Х		Хc	Х
Vital Signs d	Х	Х	Х	Х
Hematology	Х			Х
Urinalysis and drug screen	Х			Х
CYP2D6 Enzyme Activity Screening	Х			
Serum Chemistry	Х			Х
Serum Pregnancy Test (for FOCP only)	х			Х
Urine Pregnancy Test (for FOCP only)		х		
CAADID	Х			
CGI	Х	Х	Х	Х
C-SSRS	Х	Х	Х	Х
CAARS e		Х	Х	Х
Concomitant Medication	Х	Х	Х	Х
Randomization		Х		
SM Dispensed		Х	Х	
SM Diary Dispensed			Xf	
Optional SM Administered On-Site g			х	
Optional PK Blood Sampling			X h	
Adverse Events			Х	Xi

a To be obtained prior to any study procedures being performed.

b To be performed at the end of Visit 8 (unless done previously during Visit 8), or at early discontinuation.

C At Visit 4 only

d Heart rate, seated blood pressure, temperature, and respiratory rate will be measured at every visit. The vital signs readings will be performed within approximately 10 minutes prior to the scheduled blood draws, where applicable. Height will be taken at screening and weight will be assessed at each visit.

e CAARS self-report done only at Visits 2 and 8, CAARS investigator-report done at Visits 2-8

 $f \qquad \mbox{At Visit 7 to record SM taken prior to Visit 8. \ \mbox{Diary to be collected at Visit 8}.$ 

- g Dose to be administered on-site after the pre-dose draw and an overnight fast at Visit 8; subjects may eat 2 hours after dosing.
- h At Visit 8, subjects who wish to participate will be dosed after an overnight fast and have a series of PK samples drawn. Samples will be taken pre-dose, and at Hours ½, 1, 2, 3, 4, 5, and 6.
- i Any subject who experiences an adverse event (whether serious or non-serious) or has a clinically significant abnormal laboratory test value(s) will be followed by the Investigator at appropriate intervals based on the severity and nature of the event, until resolved, or when the condition is assessed as stable, causality other than the SM has been found, or the subject is referred to another health care professional.

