## 9.4.1.3. Dose Treatment Period

### 9.4.1.3.1. Visits 2-7

Dosing Schedule:

- The first dose of SM should be taken the morning following the randomization visit.
- Following dosing for a week at the starting dose of 150mg SPN-812V or placebo (1 capsule TID), subjects will be titrated to and maintained at the 300mg SPN812-V or placebo dose level (2 capsules TID) for 5 weeks.
- Subjects in the highest dose group will be permitted to down titrate to the starting dose at the Investigator's discretion in consultation with the Medical Monitor. Subjects who still cannot tolerate study medication after one down-titration should be removed from the study. Visits will occur on a weekly basis (+/- 2 days).

The following evaluations will be performed:

- AEs assessed (monitoring begins after first dose of SM)
- Administration of CGI-I
- Administration of CAARS, investigator-rated version at each visit, self-rated version only at Visit 8
- Administration of C-SSRS
- Vital signs and weight
- ECG (12-lead) (Visit 4 only)
- Assessment of concomitant medications
- SM returned and dispensed, assessment of compliance
- SM time recordation diary dispensed to subjects who have consented to participate in the PK sub study (Visit 7)
- Subjects who will participate in the optional PK sub study at Visit 8 will be reminded to not eat or take SM prior to coming to the clinic the morning of Visit 8

### 9.4.1.3.2. Visit 8

The following evaluations will be performed:

- AEs assessed
- Administration of CGI
- Administration of CAARS, investigator-rated and self-rated versions
- Administration of C-SSRS
- Vital signs and weight

- Assessment of concomitant medications
- SM returned, assessment of compliance
- SM time recordation diary collected

PK Sub study Procedures: All efficacy assessments will be done first.

- Subjects who agree to participate in the optional PK sub study will be given 2 x 50mg SPN-812V on-site in the morning, unless the subject had been down-titrated, in which case, the subject will receive 1 x 50mg SPN-812V on-site in the morning.
- Subjects must arrive after an overnight fast and may eat two hours after dosing. The subject will have a pre-dose PK draw taken, will be dosed, and will have PK draws taken at ½, 1, 2, 3, 4, 5, and 6 hours post-dose. There is a 30 minute window on all draw times, but they may be used only so that there is at least one hour between each sampling time after the ½ hour post-dose draw.

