### 9.5.5. Method of Assigning Subjects to Treatment Groups

The randomization for this study will be managed centrally; specific instructions to conduct subject randomization will be provided in a separate document to all investigational sites.

A randomization scheme will be generated using a pseudo-random number generator in a computer program. The method avoids bias by use of a chance mechanism. The randomization scheme assigns Treatment 1 or Treatment 2 to each randomization number in a 1:1 ratio.

Upon admission to the study, subjects will be assigned a 4-digit screening number, in the order that they are entered. Subjects who subsequently meet all eligibility criteria will be assigned a 6-digit randomization number. The first 3 digits will refer to the site, and the last 3 will refer to the subject-specific number, which will be assigned according to the randomization scheme.

Once a randomization number has been assigned, no attempt should be made to use that number again, if, for example, a subject is withdrawn. All subjects are randomized only once.

Note: all subjects who participate in the optional PK substudy will be given active SPN-812V capsule(s) in this portion.

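### For PK sub-study participants the end-of-study ECG and physical exam may follow the active on-site dose, and the SAP has no rule for placebo-arm safety data recorded after it

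*Protocol*

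**What the plan says.** **The dose.** Protocol 9.5.1 states: "Note: all subjects who participate in the optional PK sub study will be given active SPN-812V capsule(s) in this portion". Section 9.5.5 repeats it. Section 9.4.3 confirms that the placebo arm is meant to supply first-dose observations.

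**What must come before it.** There are two wordings. The synopsis treatment schedule says: "All rating scales will be administered prior to PK dosing and blood draws". Section 9.1.2 says that participants "will be given all efficacy assessments prior to blood draws or dosing on the PK day", and section 9.4.1.3.2 (Visit 8) says: "PK Sub study Procedures: All efficacy assessments will be done first". The synopsis PK paragraph, Protocol 9.2 and 9.4.3, and SAP 3.1.2 and 3.1.4 also name efficacy assessments only.

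**When the final safety assessments are done.** The ECG, physical exam and laboratory tests are absent from the Visit 8 list in 9.4.1.3.2 and appear in the final-visit list in 9.4.1.4. Section 9.1.3 says: "At the end of Visit 8, or prior to early discontinuation, subjects will undergo end of study assessments". The synopsis says: "At the end of the Visit 8 procedures or at early termination, subjects will complete end of study assessments". Footnote b of Table 1 says: "To be performed at the end of Visit 8 (unless done previously during Visit 8), or at early discontinuation". SAP 3.1.3 matches 9.1.3.

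**How the data are analysed.** SAP 4.2 and 6 summarise safety by the treatment actually received. SAP 6.1.1 treats every adverse event that starts or worsens after first study medication as treatment-emergent. SAP 6.4 counts QTcF outliers over all assessments in the study. Protocol 9.7.1.4.1 plans treatment-emergent event incidence by the study medication dose at first occurrence; SAP 6.1.1 does not list that table.

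**The concern.** The protocol shields the efficacy data from the PK dose but gives no matching shield to safety, which is its primary objective. A placebo subject who joins the sub-study could have the final ECG and physical exam hours after a first active dose, and those records would be tabulated as placebo at week 6.

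The final visit carries weight. It supplies one of the two scheduled on-treatment ECGs (the other is at Visit 4) and the only scheduled post-baseline physical exam. The exam shift table depends on it entirely. The synopsis safety analyses compare with placebo after six weeks of treatment, and a post-dose placebo record does not represent that condition.

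The order also mixes conditions within each arm. Completers outside the sub-study take their last dose the evening before Visit 8, while participants could be assessed soon after dosing.

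**Working it through.** **1. Order, assessment by assessment.**

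- *Rating scales and C-SSRS:* before the dose on the synopsis wording. The efficacy-only wording does not clearly cover the C-SSRS, so the two should be aligned.
- *ECG and physical exam:* no text places them before the dose. The three timing statements point to the end of the visit, and earlier completion is permitted only.
- *Labs:* same timing text, but SAP 3.6.2 asks for fasting and Protocol 9.4.3 allows food from 2 h after dosing. A fasting post-dose draw is possible but unlikely late in the day.
- *Vital signs:* on the Visit 8 list, and Table 1 footnote d places readings about 10 minutes before scheduled blood draws where applicable. The pre-dose PK sample is such a draw, so a pre-dose reading is called for. Since 7 of the 8 PK draws are post-dose, further readings are also implied, and SAP 6.3 does not name the one to summarise.
- *Adverse events:* assessed at Visit 8, but with no query fixed before the dose. SAP 6.1.1 allows for onset time not being collected, so same-day events may not be separable by clock time.

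**2. How many placebo records.** Protocol 9.2 gives 50 randomised and 20% dropout: 50 × (1 − 0.20) = 40 completers, which reproduces its stated figure. Assuming equal dropout, 40 / 2 = 20 placebo completers. The number affected is 20 × PK uptake × share of participants assessed after the dose. Neither factor is stated. With every participant assessed after the dose, uptake of 0%, 25%, 50%, 75% or 100% gives 0, 5, 10, 15 or 20. These are assumed values, not estimates.

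**3. Weight of one record.** One placebo subject whose only event or only QTcF outlier falls after the dose adds 1/25 = 4 percentage points to an overall rate, or 1/20 = 5 points to a final-visit rate. The PK sampling window is 6 h of a 42-day dosing period: 6 / (42 × 24) = 6/1008 = 0.6%. The adverse-event impact is therefore small.

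**4. Drug level, as illustration.** Protocol 9.4.3 gives a peak at about 100 min and a half-life of about 3 h (180 min). Assuming single-phase decline after the peak, the fraction of peak left at 6 h is 0.5^((360 − 100)/180) = 0.37. An assessment at the end of the PK day would be made with drug present. This says nothing about the size of any ECG or exam effect.

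**5. Level before the dose in active-arm participants.** Assume the last dose was 10 to 14 h earlier. Counting half-lives from the dose, 0.5^(10/3) = 0.10 and 0.5^(14/3) = 0.04. Counting from the 100-minute peak, 0.5^((600 − 100)/180) = 0.15 and 0.5^((840 − 100)/180) = 0.06. Either way the reading is near trough.

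**The case against.** The strongest reply is that the documents never instruct a post-dose assessment. They are silent on order relative to the dose, the end-of-visit text also covers subjects outside the sub-study, and anything already done at Visit 8 is not repeated. A site could do everything first and comply fully. That stands, and it is why the point is about what the plan permits, not what it requires.

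A reader might infer that all final-visit safety data are exposed. The documents do not support this: a pre-dose vital-signs reading is called for, and the fasting condition favours early labs.

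A reader might also infer that placebo participants would move into the active column. The synopsis safety analyses and Protocol 9.4.3 suggest that they remain placebo subjects; the SAP merely fails to say so. Nor is attribution of adverse events wholly unplanned, since the protocol's table by dose at first occurrence could help separate them. The SAP did not carry it over.

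Finally, assessing before the dose moves the scheduled final ECG of active-arm participants to near trough. That is a real cost in a safety study. It is limited, because completers outside the sub-study are already assessed after a last dose the evening before.

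**Conclusion.** The point holds for the final ECG and physical exam, and for the missing SAP rule on safety data after the PK dose. It is a lesser concern for labs. For vital signs the only gap is which Visit 8 reading is summarised. Data through Visit 7, including the Visit 4 ECG, are unaffected.

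The size is bounded but not estimable: from 0 to about 20 placebo completers, assuming equal dropout. It would be tempting to state a likely number of contaminated placebo records or a bias in the comparison. The documents support neither, because uptake, actual order and any effect size are not given. Safety p-values are descriptive (protocol synopsis and SAP 6), so no error rate is at stake. The change is worth making because safety is the primary objective, the arms are small and the correction is cheap.

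**What to change.** **Protocol.** Reconcile the synopsis, 9.1.3, 9.4.1.3.2, 9.4.1.4 and Table 1 footnote b. For PK participants, complete the end-of-study ECG, physical exam and labs, with an adverse-event query, alongside the rating scales before the on-site dose. Adverse-event collection continues afterwards, and additional ECGs remain possible under 9.4.4.6.

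**SAP 4.2 and 6.**

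- Define safety treatment as that taken before the on-site PK dose.
- Flag adverse events, ECGs, labs and vital signs recorded after it, and tabulate them separately by randomised arm.
- Where the only final record is post-dose, show the table with and without it.
- Keep all QTcF values in the outlier table, with post-PK-dose values identified.
- Restore the protocol's table of treatment-emergent events by dose at first occurrence.
- State in 6.3 that the pre-dose Visit 8 vital-signs reading is summarised.

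**Cost.** A longer fasting morning, a second adverse-event query, a few extra tables, and near-trough final records in active-arm PK participants (about 4 to 10% of the level left, counting from a dose assumed 10 to 14 h earlier). No dose changes. If the visits are already complete, the SAP changes can stand alone; SAP 8 provides an addendum route even after database lock.
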